11.3. Pregnancy

On study pregnancy, if any, will be reported in a data listing.

11.4. Overdose

All occurrences of overdosing (accidental or intentional; regardless of whether it is associated with an AE) will be reported in a data listing.

11.5. Concomitant Medications and Anticancer Therapies

All medications will be coded using the World Health Organization Drug dictionary (WHO-DD) version SEPT2015. The therapeutic class will correspond to the second level of Anatomical Therapeutic Chemical (ATC) code corresponding to the first 3 figures.

Concomitant medications, prescribed and over the counter, that the subject takes or continues to take after the date of signed Informed Consent Form will be summarized in the table. The data will be presented by treatment group and for all treated subjects. The same subject counting procedures will also apply (e.g., major class frequencies will represent subjects only once even though the same subject can be counted for multiple minor sub-classes and generic names).

The supportive individual subject data listing will be organized displaying trade and generic drug names, start and stop dates, days relative to the start of therapy, dose, frequency, route, and indication(s).

Medications will be coded using the WHO Drug Reference List Version 2015: Q1 or higher. Prior and concomitant medications will be tabulated separately according to ATC Level III and preferred name. Chemotherapies will be further summarized according to the “regimen” (combination of individual chemotherapy medications administered in a regimen irrespective of dose, route of administration or dosing schedule). The number and percent of patients receiving granulocyte colony stimulating factor (G-CSF) will be tabulated by cycle.

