10.1.2. Randomization/Start of Treatment

Following confirmation of eligibility, patients will be randomized via IXRS and should receive the first dose of study treatment (Day 1 of Cycle 1) within 3 calendar days after randomization. The maximum screening period is 28 days; eligible patients must be randomized by Day 29 of screening.

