10.1.14. Concomitant Medications and Therapies

Collect all therapies and medications, prescription and over-the-counter, from the time of signed ICF through the 30-day Safety Follow-Up Visit, including any medication used to treat AEs or SAEs during the safety follow-up period. Use of concomitant medication should be documented in the patient's source documents.

At the 30-day Safety Follow-Up Visit, collect any new anticancer therapy and the date of initiation.

During the survival follow-up period, collect only anticancer therapies.

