8.13.2. Missing Start and Stop Dates for Prior and Concomitant Medication

Incomplete concomitant medication start and/or stop dates will be imputed as follows. If either the start of medication date is completely missing or the month and/or year of the start date is missing, the start date will be set to the first dose date. If only the day is missing, the day will be set to the first day of the month except if the start month is the same as the first dose month. If the latter is true, the start day will be set to the first dose day. No imputations will be applied to the stop date. Imputed dates will be flagged in the individual supportive subject data listings.

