9.6.2. Prior and Concomitant Medications

Prior and concomitant medications will be summarized for the AT population. The patients are summarized using counts and percentages. All concomitant medications and therapies will be coded using WhoDDE (September 2015) and summaries will use the system organ class and preferred term codes, as appropriate.

All medications, prescription and over-the-counter, from the time of signed ICF through the 30-day Safety Follow-Up Visit, will be collected and summarized in the tables. This will include any medication used to treat AEs or SAEs during the safety follow-up period. Summarization will be performed separately for prior and concomitant medications (two different tables).

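### SAP 11.5 counts concomitant medication from consent, the date collection starts, so screening-only drugs enter the by-arm table and no visible rule separates prior from concomitant use

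*SAP*

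**What the plan says.** SAP 11.5 describes the concomitant table as covering prescribed and over-the-counter medications "that the subject takes or continues to take after the date of signed Informed Consent Form will be summarized in the table". The table is presented by treatment group and for all treated subjects. First dose does not appear in that sentence. Further down, the same section adds: "Prior and concomitant medications will be tabulated separately according to ATC Level III and preferred name".

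Collection starts at consent. Protocol 10.1.14 instructs sites: "Collect all therapies and medications, prescription and over-the-counter, from the time of signed ICF through the 30-day Safety Follow-Up Visit". SAP 4.5.7 repeats this window, and SAP 9.6.2 states that all medications "from the time of signed ICF through the 30-day Safety Follow-Up Visit, will be collected and summarized in the tables". SAP 9.6.2 then requires a split: "Summarization will be performed separately for prior and concomitant medications (two different tables".

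None of the visible sections defines prior medication. SAP 8.13.2, on incomplete dates for prior and concomitant medication, says that when the start date, or its month or year, is missing, "the start date will be set to the first dose date".

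On timing, Protocol 10.1.2 says: "The maximum screening period is 28 days; eligible patients must be randomized by Day 29 of screening". First dose should follow "within 3 calendar days after randomization".

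**The concern.** A prior/concomitant split needs a dividing date inside the collection window. SAP 11.5 places its date at the very start of that window, so the concomitant criterion takes in essentially every general medication collected, including drugs the patient had stopped before any study drug was given. The separate prior table that the SAP orders twice is then left without a rule.

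What is at stake is the reading of the concomitant table. It sits in the safety section and is shown by arm, so readers will look there for antiemetic, antidiarrhoeal, antibiotic and transfusion use alongside the adverse events. Use confined to screening precedes treatment and should be similar in both arms. Adding it to both columns raises both counts and can blur a real difference. Two programmers working from the same SAP could also produce different prior and concomitant tables.

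**Working it through.** The plan states no figure on this point, so there is none to reproduce. The check is a classification, plus one sum for the length of the pre-dose period.

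**Inputs**
- Start of collection: consent (Protocol 10.1.14; SAP 4.5.7 and 9.6.2). Footnote 10 of the study schedule in both documents words the end of collection differently, but the start is the same.
- Criterion for the concomitant table: taken or continued after the consent date (SAP 11.5).
- Consent to randomization: up to 28 days; randomization to first dose: up to 3 calendar days (Protocol 10.1.2).
- Day 1 of treatment: date of first dosing (SAP 8.5).

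**Classification of records that fall in the collection window**

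| Medication use | Consent date as cut (SAP 11.5 as written) | First dose as cut |
|---|---|---|
| 1. Started before consent, used after it, stopped before first dose | Concomitant | Prior |
| 2. Started and stopped between consent and first dose | Concomitant | Prior |
| 3. Started before first dose, ongoing at first dose | Concomitant | Concomitant |
| 4. Started on or after first dose | Concomitant | Concomitant |

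With the consent date as the cut, 4 of 4 types are concomitant and 0 of 4 are prior only. The one exception is a drug last used on the consent date itself. With first dose as the cut, 2 are prior only and 2 are concomitant. The two rules differ only for types 1 and 2. A drug carried over past first dose is concomitant either way and causes no distortion.

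**Length of the pre-dose period**

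Maximum consent-to-first-dose interval = 28 + 3 = 31 days. This takes screening to begin at consent and uses both allowances in full. It is a ceiling; the documents do not give the typical interval.

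**Sections side by side**
- SAP 9.6.2 takes medications collected from consent onward and divides them into two tables. As two distinct sets, that division has content only if the cut falls after consent.
- SAP 11.5 asks for the same separation but names no date other than consent.
- SAP 8.7 assigns concomitant medications in the listings to cycles that begin on Day 1 of each cycle. A type 1 or type 2 record meets the 11.5 criterion but falls in no cycle under that scheme. SAP 8.7 governs listings, so it does not supply the missing rule for the tables.

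**The case against.** The strongest reply is that the sentence in SAP 11.5 was never meant as a definition. It may simply repeat the collection window, and a reading that defeats a table ordered in the same section is uncharitable. This may well explain the wording. It does not supply a cut date, and a programmer who follows the sentence literally will misclassify screening-only drugs.

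The second reply concerns redaction. SAP 8.7 refers to the Data Handling Guidance for the cycle assignment of concomitant medications, and that text is not public. A first-dose rule may exist there, so its absence from the whole plan cannot be asserted. But the reference concerns listings, and the visible text of 9.6.2 and 11.5 does not send the reader there for the tables. If such a rule exists, 11.5 still states a different one.

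The third reply is that little is harmed, and this largely stands. Protocol 13.3.3 places the focus of the safety evaluation on adverse events and laboratory data. No between-arm test of medication use is planned. G-CSF use is tabulated by cycle, prior anticancer therapy has its own summary in SAP 9.6.1, and the listing shows days relative to the start of therapy, so screening-only use can be seen there.

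A reader might go further in four ways that the documents do not support:
- *The prior table will be nearly empty.* This assumes that prior and concomitant exclude each other. The SAP does not say so. If prior meant anything started before first dose, the table would have entries, although screening-only drugs would still also count as concomitant.
- *The table presents screening drugs as on-treatment use.* The SAP does not use that label.
- *SAP 11.5 contradicts the imputation rule in 8.13.2 and the TEAE window in 11.1.2.* Both start from first dose, but both are compatible with either cut for medications.
- *The contrast between arms is heavily diluted.* Any such ratio depends on assumed rates of screening-only and later use, and the documents give neither.

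**Conclusion.** The point holds as a minor one. SAP 11.5 ties the concomitant table to the date on which collection begins. Followed literally, it brings in medication used only before first dose, over at most 31 days per patient, and leaves the required prior/concomitant separation without a visible rule.

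The consequence is confined to counts in a descriptive safety table. Some weakening of the visible difference between arms in supportive medication is possible and is probably modest; its size is unknown. OS, PFS, the type I error and TEAE incidence do not change.

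The conclusion rests on reading 11.5 as written and on no rule in the redacted Data Handling Guidance overriding it. If the Guidance does hold a first-dose cut, what remains is a wording error in 11.5.

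**What to change.** In SAP 9.6.2 and 11.5, state one pair of definitions. Prior medication is medication stopped before the first dose date. Concomitant medication is medication taken or continued on or after the first dose date, through the 30-day Safety Follow-up Visit. Medication used only between consent and first dose then belongs in the prior table. Because SAP 8.13.2 does not impute stop dates, a clause should say how a record with a missing or partial stop date is classed. Check that the Data Handling Guidance uses the same cut.

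The cost is two sentences of SAP text and one date comparison in the programs. The first dose date is already used elsewhere in the SAP, so no new data are needed and the protocol's collection window can stay as it is.

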11.6. Clinical Laboratory Data

All laboratory values will be converted to SI units and classified as normal, low, or high based on normal ranges (converted to SI units if needed) supplied by the laboratory performed the test. Laboratory categories will be expressed in terms of the L (below LLN), N (between LLN and ULN) and H (above ULN) classifications for numerical measurements and normal, abnormal for characteristic measurements. Additionally, abnormal laboratory values will be presented according to the NCI CTCAE v4.3 laboratory toxicity grades. All laboratory data will be coded with CTCAE grade, where CTCAE grading is available. Local laboratory ranges will be used for grading. In the event a range is not available a standard set of lab ranges as detailed in **CCI** will be utilized and flagged in the database.

Tables of descriptive statistics for hematology, biochemistry and urinalysis will be presented. Summary statistics (descriptive statistics) for quantitative laboratory parameters will include number of subjects, mean, standard deviation, median, minimum and maximum. Continuous parameters will be summarized for the actual and change from baseline values for all available parameters and study visit time points. Categorical results will be represented by shift tables (by visit) for the tests where NCI CTCAE grading is not available.

Changes in the NCI CTCAE grade from baseline to the worst grade recorded post-baseline will be tabulated in the form of shift tables. Applicable bi-directional laboratory tests will be represented as one artificial one-directional tests, where hypo- part (below the LLN) will be assigned with negative signs and hyper- part (above the ULN) will continue to keep positive values. Therefore, valid grades for this artificial test will cover span from -4 to +4, where Grade 0 will correspond to

the values lying within the normal range. The definition of hypo- and hyper-toxicity grades follows the definition provided by the NCI CTCAE v4.3 definition document. Laboratory tables with CTCAE grading will only be produced for laboratory parameters for which CTCAE grading is available. An overall shift summary will also be provided comparing baseline to worst post-dose toxicity observed across all visits.

The number and percentage of patients with laboratory abnormalities of Grade 3 or Grade 4 that worsened from baseline by ≥ 1 grade or are missing at baseline will be summarized. For patients with more than 1 value recorded in a cycle/group of cycles, the abnormality with the highest grade will be selected for tabulation.

Time to event/worst grading will be assessed for selected clinical tests (hemoglobin, neutrophils, platelets) where CTCAE grading is available. The time to event/worst grading is defined as time from the date of the first dose of study medication to the date of the first occurrence of worst post-baseline CTCAE grade. If multiple events of the same worst grading occur, the earliest occurrence will be used. If no abnormal post-baseline values were recorded, the time to event/worst grading will be censored.

Presentation of the time to event/worst grading will be based on the Kaplan-Meier product-limit method is applied to estimate the mean, standard deviation, median, 25% percentile, and 75% percentile of the time to event/worst grading.

All observed (including unscheduled) laboratory parameters will be listed. The supportive listings for hematology, serum chemistry, and urinalysis will include the subject number, subject age and sex; laboratory test, lab test units, lab test result, and the lower and upper limits of normal (provided by the local laboratory where the test was performed); sample collection date, time of collection, and relative day; type of visit. The listing will be sorted by laboratory parameter, subject number, and by time points within laboratory parameter and subject number. Abnormal results will be flagged based on the categories mentioned above.

Specific rules how to handle clinical laboratory data can be found in the .

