11.6.1. Hematology

The following test will be summarized and tabulated, all other hematology tests will be listed only:

Red blood cells count (RBC)	White Blood Cells (WBC)	
Hemoglobin	Neutrophils (absolute value)	Neutrophils (%)
Hematocrit	Lymphocytes (absolute value)	Lymphocytes (%)
Platelets	Monocytes (absolute value)	Monocytes (%)
	Eosinophils (absolute value)	Eosinophils (%)
	Basophils (absolute value)	Basophils (%)

The “most extreme value” recorded, and the corresponding number of days to the most extreme value recorded, will be summarized descriptively for Grade 3 or 4 abnormalities. This will be limited to the following selected “parameters of interest”: hemoglobin, neutrophils and platelets for the “most extreme” is defined as the value of smallest magnitude. Additional parameters may be added to this analysis as appropriate.

The median number of days to ‘recovery’ (Section 8.10) in patients with Grade 3 or 4 abnormalities that worsened from baseline will be obtained from Kaplan-Meier estimates.

Shift tables showing changes in the NCI CTCAE grade from baseline to the worst grade recorded post-baseline are tabulated. Parameters with NCI CTCAE criteria defined bi-directionally have low value abnormalities represented by a negative sign so that they may be differentiated from high value abnormalities. If the NCI CTCAE criteria are uni-directional the negative sign is not used even if the criteria are defined to flag low value abnormalities.

The rate per 100 patient years (see Section 8.9 for the appropriate details) of Grade 3 or 4 abnormalities in hemoglobin (low), neutrophils, and platelets, along with the corresponding 95% Poisson CIs, will be summarized.

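### One signed grade per bi-directional laboratory test shows only one direction in the shift tables for a patient with both low and high abnormalities

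*SAP*

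**What the plan says.** SAP 11.6 (Clinical Laboratory Data) sets up the scale in its account of grade shifts: "Applicable bi-directional laboratory tests will be represented as one artificial one-directional tests, where hypo- part (below the LLN) will be assigned with negative signs". High values keep positive grades, and zero stands for a result inside the normal range. The outcome is stated: "Therefore, valid grades for this artificial test will cover span from -4 to +4". SAP 11.6.1 (Hematology) repeats the convention: "Parameters with NCI CTCAE criteria defined bi-directionally have low value abnormalities represented by a negative sign". It gives the reason, which is to tell low abnormalities from high ones, and it uses no sign for tests whose criteria run in one direction only.

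The signed grade is then reduced to one value per patient: "Changes in the NCI CTCAE grade from baseline to the worst grade recorded post-baseline will be tabulated in the form of shift tables". The same reduction is applied over the whole study: "An overall shift summary will also be provided comparing baseline to worst post-dose toxicity observed across all visits".

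A separate paragraph of SAP 11.6 gives patient counts for one class of result: "laboratory abnormalities of Grade 3 or Grade 4 that worsened from baseline by ≥ 1 grade or are missing at baseline will be summarized". When a cycle or group of cycles holds several values, "the abnormality with the highest grade will be selected for tabulation". That paragraph mentions neither sign nor direction.

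The visible text does not say how two abnormalities of equal grade in opposite directions are resolved, or whether worsening is measured within a direction. It points to further laboratory rules, but that reference is removed from the public copy.

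**The concern.** Low and high values of the same analyte are different toxicities. Once they share one grade and one worst value is kept, the shift table can describe only one of them. The other direction is under-counted, by arm, for every patient who has both.

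The second issue is conditional. A rule that asks for worsening by at least one grade is clear on a one-directional scale. On a merged scale it has to compare a baseline in one direction with a result in the other. If only size is compared, a new severe low value that follows an equally severe high baseline shows no change.

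What is at stake is the accuracy of patient-level laboratory counts. Safety and tolerability is listed as a key secondary objective (protocol section 7, SAP 3.1.2). No efficacy test, alpha level or sample size is involved.

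**Working it through.** The plan gives no figure to reproduce here. The check enumerates the grade patterns that the stated scale allows, reading *worst* and *worsened* by magnitude, which is the sensible reading.

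**Inputs.** Low grades 1 to 4 and high grades 1 to 4 (SAP 11.6 scale); one worst grade kept per patient (SAP 11.6 shift tables); worsening means a rise of at least one grade (SAP 11.6, Grade 3/4 paragraph).

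**Step 1: both directions occur after baseline.** Let L be the worst low grade and H the worst high grade. There are 4 × 4 = 16 pairs.
- H > L, so the low grade is lost: 3 + 2 + 1 = 6 pairs.
- L > H, so the high grade is lost: 6 pairs.
- H = L, with no visible rule: 4 pairs.
- Total: 6 + 6 + 4 = 16. In all 16, one kept grade can show only one direction.

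For a low Grade 3 or 4 together with any high grade there are 2 × 4 = 8 pairs. The low grade is lost in 1 (-3 with +4), tied in 2 (-3 with +3, -4 with +4) and kept in 5. By symmetry the same holds for a high Grade 3 or 4.

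**Step 2: the direction switches from baseline and ends in Grade 3 or 4.** Let b be the size of the baseline grade (1 to 4) and p the size of the later grade in the opposite direction (3 or 4). There are 4 × 2 = 8 patterns each way, 16 in all. The rule is p - b ≥ 1.
- p = 3 counts for b = 1 and 2; p = 4 counts for b = 1, 2 and 3. That is 5 each way, so 10 of 16 count.
- Missed: 3 to 3, 4 to 3 and 4 to 4, each way, so 6 of 16. For +3 to -3 the difference is 3 - 3 = 0.

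This step applies only if the Grade 3/4 table uses the merged grade. The shift table itself can show such a switch, because it keeps the sign at baseline and afterwards.

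**Step 3: separate low and high grades.** Each of the 16 pairs in Step 1 shows both grades, so all 8 low Grade 3/4 patterns are kept and ties no longer arise. In Step 2 the baseline in the new direction is 0, so the change is 3 - 0 = 3 or 4 - 0 = 4, and all 16 switches count.

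**Step 4: which outputs are exposed.** SAP 11.6.1 gives low hemoglobin, neutrophils and platelets a rate of Grade 3 or 4 abnormalities per 100 patient-years, and takes the smallest value as most extreme. SAP 11.6.2 (Serum Chemistry) has no comparable direction-specific summary; its panel includes sodium, potassium, calcium and glucose. The SAP does not list which tests it treats as bi-directional, so placing these four among them is an assumption.

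**The case against.** The strongest reply is that the deciding rules may exist out of sight. SAP 11.6 refers to laboratory handling rules that are not in the public copy, SAP 8.8 sends multiple assessments to a data handling guidance, and SAP 14 records an added appendix on safety data. That stands for ties and for the meaning of *worst*, and the gap in the public text is not an error in the plan. It does not answer the main point: the visible text merges the two directions and tabulates one worst grade, and showing both would need tables other than those described.

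A second reply is that low and high values remain visible elsewhere. Results are classified as low, normal or high, minima and maxima are summarized, every value is listed, and abnormalities with clinical impact are reported as adverse events unless they support a diagnosis already reported (protocol 12.2.1). This is true and limits the harm. None of these outputs gives a complete count of patients by laboratory grade and direction.

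A reader might infer two stronger claims.
- **That *highest* means the signed maximum**, so that +1 outranks -3. A low Grade 3/4 would then be lost in 8 of 8 patterns, and every high-to-low switch (8 of 16) would fail the worsening rule. The documents do not support this. SAP 11.6.1 uses the sign as a label of direction, and on a signed maximum a normal value of 0 would outrank -4, which would defeat that purpose.
- **That a switch of direction is never counted as worsening.** The SAP has no such rule. By magnitude 10 of 16 switches count, and if any signed difference of at least one grade counts, all 16 do.

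It is also fair to say that the Grade 3/4 paragraph does not itself invoke the signed scale, so that link is an inference.

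**Conclusion.** The point holds in a limited form. As described, the shift tables count only one direction for a patient with both low and high abnormalities on a merged test, and equal-magnitude ties have no visible rule. By magnitude the loss falls equally on the two directions (6 and 6 of 16 pairs, with 4 ties). The further risk, that a new Grade 3/4 abnormality is missed after an opposite-direction baseline of equal or higher grade (6 of 16 switch patterns), depends on the Grade 3/4 table using the merged grade.

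These are counts of possible patterns. How many patients would show them is not in the documents, so no rate of under-counting can be given. Neutrophils and platelets are unaffected if they are treated as uni-directional, which is an assumption. Hemoglobin appears to be treated as bi-directional, since one summary specifies its low side; that rate and the lowest-value summary protect it there. What remains is a cheap improvement to descriptive safety tables, mainly serum chemistry.

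**What to change.** In SAP 11.6 and 11.6.1, derive two one-directional grades for each bi-directional test, low 0-4 and high 0-4. For each direction, treat a baseline abnormality in the opposite direction as Grade 0; the existing handling of a missing baseline can stay. Tabulate the worst post-baseline grade, the shift from baseline, worsening of at least one grade and the Grade 3/4 counts separately for low and high. State which tests are treated as bi-directional, and say that the Grade 3/4 table follows the same rule.

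The cost is SAP wording, some reprogramming and more table rows. No new data are needed.

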 - a. Absolute neutrophil count (ANC) of $\geq 1,500/\text{mm}^3$ (ie, $\geq 1.5 \times 10^9/\text{L}$ by International Units [IU]).
 - b. Platelet count $\geq 100,000/\text{mm}^3$ (IU: $\geq 100 \times 10^9/\text{L}$).
 - c. Hemoglobin value of ≥9.0 g/dL prior to randomization based on measurements obtained 2 weeks or more after last transfusion received.
 - d. Aspartate aminotransferase (AST; SGOT) and alanine aminotransferase (ALT; SGPT) \leq 3.0 × upper limit of normal (ULN); if liver function abnormalities are due to underlying liver metastasis, AST (SGOT) and ALT (SGPT) \leq 5 × ULN.
 - e. Total serum bilirubin of $\leq 1.5 \times ULN$ (except for Grade 1 hyperbilirubinemia due solely to a medical diagnosis of Gilbert's syndrome).
 - f. Serum creatinine $\leq 1.5 \text{ mg/dL}$.
- 9. Is willing and able to comply with scheduled visits, treatment plans, laboratory tests, and other study procedures.
- 10. Women of childbearing potential must have a negative pregnancy test (urine or serum) within 7 days prior to starting the study drug. Both males and females must agree to use effective birth control during the study (prior to the first dose and for 6 months after the last dose) if conception is possible during this interval. Female patients are considered to not be of childbearing potential if they have a history of hysterectomy, or are postmenopausal defined as no menses for 12 months without an alternative medical cause. For both males and females, see Section 8.8.3 for definitions of contraceptive methods considered effective for this protocol.

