8.3.2. Exclusion Criteria

Exclude a patient from this study if any of the following conditions are observed:

- 1. Has a serious illness or medical condition(s) including, but not limited to the following:
 - a. Other concurrently active malignancies excluding malignancies that are disease free for more than 5 years or carcinoma-in-situ deemed cured by adequate treatment.
 - b. Known brain metastasis or leptomeningeal metastasis.
 - c. Active infection (ie, body temperature ≥38°C due to infection) including active or unresolved pneumonia/pneumonitis.
 - d. Intestinal obstruction, pulmonary fibrosis, renal failure, liver failure, or cerebrovascular disorder.
 - e. Uncontrolled diabetes.
 - f. Myocardial infarction within 12 months prior to randomization, severe/unstable angina, symptomatic congestive heart failure New York Heart Association (NYHA) class III or IV
 - g. Gastrointestinal hemorrhage (Grade ≥ 3) within 2 weeks prior to randomization.
 - h. Known human immunodeficiency virus (HIV) or acquired immunodeficiency syndrome (AIDS)-related illness, or chronic or acute hepatitis B or hepatitis C.
 - Patients with autoimmune disorders or history of organ transplantation who require immunosuppressive therapy.

- j. Psychiatric disease that may increase the risk associated with study participation or study drug administration, or may interfere with the interpretation of study results.
- 2. Has had treatment with any of the following within the specified time frame prior to randomization:
 - a. Major surgery within prior 4 weeks (the surgical incision should be fully healed prior to study drug administration).
 - b. Any anticancer therapy within prior 3 weeks.
 - c. Extended field radiation within prior 4 weeks or limited field radiation within prior 2 weeks.
 - d. Any investigational drug/device received within prior 4 weeks.
- 3. Has previously received TAS-102.
- 4. Has unresolved toxicity of greater than or equal to CTCAE Grade 2 attributed to any prior therapies (excluding anemia, alopecia, skin pigmentation, and platinum-induced neurotoxicity).
- 5. Is a pregnant or lactating female.
- 6. Is inappropriate for entry into this study in the judgment of the Investigator.
- 7. Known or assumed hypersensitivity to TAS-102 or any of its ingredients.

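### Time to worst grade in SAP 11.6 counts unchanged entry anaemia as an event and dates worsening patients later, so the haemoglobin median can be later on the more myelosuppressive arm

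*SAP*

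**What the plan says.** SAP Section 11.6 plans a time to event/worst grading summary for haemoglobin, neutrophils and platelets. The time is "time from the date of the first dose of study medication to the date of the first occurrence of worst post-baseline CTCAE grade"; repeats of the same worst grade take the earliest date. On censoring it says only this: "If no abnormal post-baseline values were recorded, the time to event/worst grading will be censored". No censoring date is given. The output is descriptive: the "Kaplan-Meier product-limit method is applied to estimate the mean, standard deviation, median, 25% percentile, and 75% percentile" of that time. Protocol Section 13.3.3 asks for worst severity grade and time to event but does not define the event.

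In the same SAP section, the Grade 3/4 tabulation is limited to abnormalities that "worsened from baseline by ≥ 1 grade or are missing at baseline". The recovery analysis (SAP 8.10 and 11.6.1) also has a worsening condition. The time-to-worst-grade rule has none.

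Entry rules matter here. Protocol Section 8.3.1 requires "Hemoglobin value of ≥9.0 g/dL prior to randomization". Protocol Section 8.3.2 excludes unresolved toxicity of Grade 2 or higher from prior therapy, "excluding anemia, alopecia, skin pigmentation, and platinum-induced neurotoxicity". Laboratory values are classed low, normal or high against local ranges (SAP 11.6). The first scheduled post-baseline haematology sample is Day 15 of Cycle 1; later ones precede Day 1 of each cycle (SAP 4.5.3.1).

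**The concern.** The rule has two features that pull the wrong way.

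- **Overlap with entry.** Any abnormal post-baseline value makes the patient an event, whatever the baseline grade. Haemoglobin that was low at entry and stays low, or improves but remains below the normal limit, is an event at the first sample.
- **Looking ahead.** The event date is known only once all of a patient's samples are in. If the count keeps falling, the date moves to the later, worse value. A patient observed for a shorter time has less opportunity for that, so exposure also enters the result.

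Both push the median earlier on placebo and later on the arm where counts keep falling. Safety and tolerability is listed among the key secondary objectives (Protocol Section 7), and the earlier Phase 2 gastric study had Grade 3 or 4 neutropenia in 69.0% and anaemia in 20.7% (Protocol 6.1.2.2). A reader who takes this median as onset of anaemia could draw the wrong conclusion about which arm becomes anaemic sooner.

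**Working it through.** The plan states no figure for this analysis, so there is none to reproduce.

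**Step 1. The rule applied by hand.** With no cycle delays the samples fall on Day 15, Day 29 (1 + 28) and Day 57 (1 + 56).

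| Patient | Baseline | Day 15 | Day 29 | Day 57 | Event under SAP 11.6 |
|---|---|---|---|---|---|
| A, unchanged | 1 | 1 | 1 | 1 | Day 15 |
| B, improves | 2 | 1 | 1 | 1 | Day 15 |
| C, worsens stepwise | 1 | 1 | 2 | 3 | Day 57 |

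C has the worst course and the longest time. This follows from the definition alone.

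**Step 2. Grade-transition model.** Illustrative, 20,000 patients per arm. Assumed: baseline grade mix; chance of worsening per visit of 25%, 35% or 50% on TAS-102, paired with 5%, 8% or 10% on placebo; treatment either longer on TAS-102 or equal. Kaplan-Meier medians under the SAP rule, in days, over the three pairs:

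| Baseline mix | Exposure | TAS-102 | Placebo |
|---|---|---|---|
| 60% Grade 1, 20% Grade 2 | longer on TAS-102 | 29 to 57 | 15 |
| 60% Grade 1, 20% Grade 2 | equal | 29 | 15 |
| 40% Grade 1, 10% Grade 2 | longer on TAS-102 | 57 | 29 |
| 40% Grade 1, 10% Grade 2 | equal | 29 | 29 to 57 |
| all normal | longer on TAS-102 | 57 to 85 | 169 to not reached |
| all normal | equal | 57 to 85 | 169 to 309 |

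With the 60/20 mix, 55% to 67% of all placebo patients are events without any worsening. With normal baselines the order is right, but looking ahead still costs time: in the 35%/8% pair with longer TAS-102 exposure, the TAS-102 median is 85 days against 29 for first worsening of at least 1 grade, while placebo is 197 under both.

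**Step 3. Haemoglobin-path model.** Assumed: baseline mean 11, SD 1.2, floor 9.0 g/dL; lower limit of normal 12; grade cuts 10 and 8; median treatment 50 days placebo, 80 days TAS-102; fall per cycle 0.1 g/dL placebo, and 0.3, 0.5 or 0.8 on TAS-102.

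- Placebo: 88% have an event and 74% of those are no worse than baseline, so 0.88 × 0.74 = 65% of placebo patients. Median 15 days.
- TAS-102: median 29, 57 and 57 days. Grade 3 occurs in 11%, 29% and 49%, against 0.4% on placebo. The Phase 2 figure of 20.7% lies between the 0.3 and 0.5 falls; the 0.8 fall is beyond it.
- Equal 50-day treatment, fall 0.5: TAS-102 median 29 days.
- With exponential treatment time, between-patient slope variation and 0.4 g/dL noise: 15, 29 and 29 days on TAS-102 against 15 on placebo; with equal exposure, 15 in both arms.
- Baseline means 11 to 11.75, longer TAS-102 exposure: 15 to 29 days placebo, 29 to 85 TAS-102.
- Baseline mean 12.5, equal exposure: 57 days TAS-102, 85 placebo, the expected order.

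The assumed means imply the following share below 12 g/dL at entry, from [Φ((12 − m)/1.2) − Φ((9 − m)/1.2)] / [1 − Φ((9 − m)/1.2)]:

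- m = 11: (0.798 − 0.048)/0.952 = 79%
- m = 11.75: (0.583 − 0.011)/0.989 = 58%
- m = 12.5: (0.339 − 0.002)/0.998 = 34%

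**Step 4. Other definitions.** In the 60/20, 35%/8% scenario with longer TAS-102 exposure, first worsening of at least 1 grade gives 29 days TAS-102 against 309 placebo. First Grade 3 or higher that worsened gives 113 days against not reached. Both put the more toxic arm earlier.

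**The case against.** The other side has real weight.

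- **The summary is descriptive.** No between-arm test is planned for it and no curves are mentioned. The SAP calls it time to worst grading, and patient C did reach the worst grade on Day 57. This stands, but a Kaplan-Meier median by arm will be read as timing of toxicity.
- **Other outputs cover the ground.** Shift tables show Grade 1 to 1 and 2 to 2 directly. Grade 3/4 rates per 100 patient-years use a fixed threshold and time at risk to first onset (SAP 8.9, 11.6.1). These limit the harm without correcting this row.
- **It is mainly a haemoglobin problem.** Entry requires neutrophils of at least 1,500/mm³ and platelets of at least 100,000/mm³, and anaemia is the only blood-count toxicity exempted. A reader might infer that timing is reversed for all three tests. The documents do not support that; entry limits make normal baseline counts likelier for the other two, though grading against local ranges does not guarantee it.
- **Size and direction rest on assumptions.** Neither document gives baseline haemoglobin. A reader might infer that the plan will show anaemia later on TAS-102. It can; the checks above also give ties and the expected order.
- **Redaction.** SAP 11.6 refers to a removed reference for laboratory handling, and SAP Section 14 mentions an appendix of data handling rules for safety endpoints. A baseline condition or censoring date may be there. No visible text supplies one.

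**Conclusion.** The point holds for the visible rule. Without a worsening condition or a fixed grade, unchanged entry anaemia is an event at about Day 15 and a stepwise-worsening patient is dated later. The haemoglobin median can then be later on the more myelosuppressive arm. Whether it is depends on how common baseline anaemia is and on relative exposure: reversal or tie at assumed baseline means of 11 to 11.75 g/dL, mostly the expected order at 12.5. Where baseline counts are normal no reversal is expected.

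This does not put the trial's safety conclusion as a whole in doubt. OS, PFS, the shift tables and the Grade 3/4 rates are unaffected. It is one descriptive safety summary that should be corrected because it can mislead and is cheap to repair.

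**What to change.** Redefine the event in SAP 11.6 as the first post-baseline value of Grade 3 or higher that is at least 1 grade worse than baseline or has a missing baseline. That is the condition the section already uses for its Grade 3/4 tabulation. Censor other patients at the last post-baseline sample for that test. Keep days to the most extreme value only as the descriptive Grade 3/4 summary already in SAP 11.6.1, and do not present time to worst grade as onset of toxicity. If the redacted appendix already contains a baseline condition or censoring date, state it in Section 11.6.

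The cost is a wording change and one derivation on data already collected, to be settled before unblinding. The downside is fewer events, so the median may not be reached, mainly on placebo. In the Step 4 scenario, 41% of TAS-102 and 5% of placebo patients had an event under this kind of definition. The event rate and lower quartile would then carry more of the information than the median.
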